6.6. Data Handling and Transformations

By-subject listings will be presented and sorted by treatment group, actual baseline ordinal score, subject number, and study day (if applicable). Data collected on log forms, such as AEs, will be presented in chronological order and alphabetical order using the preferred term within subject. The intervention stage and treatment arm to which subjects were randomized will be used in the listings.

In general, age (in years) on the date of Study Day 1 will be used for analyses and presentation in demographic data listings. If an enrolled subject was not dosed with study product at all, the date baseline assessment was conducted will be used instead of the first dosing date of study product. For screen failures, the date the informed consent was signed will be used for age calculation. If only the birth year is collected on the case report form (CRF), “01 January” will be used for the unknown birthday and month for the purpose of age calculation, unless age is captured on the CRF.

The conventions for missing dates (adverse event [AE], concomitant medication [CM], medical history [MH]) are provided in [Table 8](#).

Table 8: Partial Date Imputation for Adverse Events (AEs), Concomitant medications (CMs), and Medical History (MH)

Type of Date	Scenario			Impute strategy
	Month	Day	Year	
AE Dates				
AE Start Date	UNK	UNK	UNK	IMPUTE with FIRST_DOSE; Default to making AE start date/time a treatment emergent event and earliest possible date. Impute with randomization date if not treated, or informed consent date for other subjects. In case that imputed start date is after stop date, impute as stop date.
AE Start Date	UNK	UNK	YYYY	IMPUTE with 01/01/YYYY, or FIRST_DOSE (or randomization date if not treated) date if in same year. In case that imputed start date is after AE stop date, impute as stop date.
AE Start Date	MM	UNK	YYYY	IMPUTE with MM/01/YYYY, or FIRST_DOSE (or randomization date if not treated) if it is in same month/year. In case that imputed start date is after AE stop date, impute as stop date.
AE Stop Date	UNK	UNK	UNK	IMPUTE with discharge date, or last assessment date if never discharged or last assessment is after discharge date
AE Stop Date	UNK	UNK	YYYY	If discharge date or last assessment date is YYYY, IMPUTE with discharge date if discharged, or last assessment date if never discharged. If discharge date or last assessment date is YYYY+1 then IMPUTE AE Stop date as 12/31/YYYY.
AE Stop Date	MM	UNK	YYYY	IMPUTE with last day of MM/YYYY or last assessment day if never discharged or last assessment month/year is the same as MM/YYYY
CM Dates				
CM Start Date	UNK	UNK	UNK	IMPUTE with FIRST_DOSE date; Default = make CM start date/time a CM with earliest possible date; Impute with randomization date if not treated, or informed consent date for other subjects. In cases with imputed start date after stop date, impute start date as stop date.
CM Start Date	UNK	UNK	YYYY	IMPUTE with 01/01/YYYY, or FIRST_DOSE date (or randomization date if not treated) if in same year; if first dose is later in that year, start date= 01/01/YYYY. In cases with imputed start date after CM stop date, impute start date as stop date.
CM Start Date	MM	UNK	YYYY	IMPUTE with MM/01/YYYY, or FIRST_DOSE (or randomization date if not treated) if it is in same month/year. In case that imputed start date is after CM stop date, impute start date with stop date.
CM Stop Date	UNK	UNK	UNK	IMPUTE with discharge date, or last assessment date if never discharged or last assessment date is after discharge date
CM Stop Date	UNK	UNK	YYYY	If discharge date or last assessment date is YYYY, IMPUTE with discharge date if discharged, or last assessment date if never discharged. If discharge date or last assessment date is YYYY+1 then IMPUTE AE Stop date as 12/31/YYYY.
CM Stop Date	MM	UNK	YYYY	IMPUTE with last day of MM/YYYY or last assessment day if never discharged or last assessment month/year is the same as MM/YYYY
MH Dates				
MH Start Date	UNK	UNK	UNK	IMPUTE with FIRST_DOSE date; Default = make MH start date/time a MH with earliest possible date. Impute with randomization date if not treated, or informed consent date for other subjects. In case that imputed start date is after stop date, impute start date with stop date.
MH Start Date	UNK	UNK	YYYY	IMPUTE with 01/01/YYYY
MH Start Date	MM	UNK	YYYY	IMPUTE with MM/01/YYYY
MH Stop Date	UNK	UNK	UNK	IMPUTE with discharge date, or last assessment date if never discharged or last assessment date is after discharge date
MH Stop Date	UNK	UNK	YYYY	IMPUTE with 12/31/YYYY
MH Stop Date	MM	UNK	YYYY	IMPUTE with last day of MM/YYYY

Listings should not present imputed dates; listings should present partial dates or “.” if date is entirely missing.

6.7. Multicenter Studies

Data will be pooled across all clinical sites. Center effects are not anticipated because the sites are using standardized procedures for collection of data.

Nevertheless, to guard against the potential for regional differences, a sensitivity analysis for the primary endpoint will adjust for site effects pooling sites together based on their geographic region.

6.8. Multiple Comparisons/Multiplicity

Analyses related to primary and key secondary endpoints will be conducted without adjustment for multiple endpoints and multiple arms. That is, all planned analyses will be conducted without statistical adjustment for multiplicity, with the main focus on the primary and secondary endpoints for each intervention versus placebo comparison.

However, a possible set of supplementary analyses described in the remainder of this section adjusting for multiplicity might be performed, but only if their inclusion appears likely to be helpful in interpreting the primary and secondary analyses results.

For this approach, adjusted p-values for multiple endpoints (primary and secondary continuous and binary endpoints) will be computed using the Westfall-Young permutation approach (specifically, the free step-down resampling method procedure that produces adjusted p-values that preserves the order of the endpoints for the unadjusted p-values) and results will be reported in [Table 44](#). Two analyses will be performed both based on complete data, one treating Day 8 ordinal score as a continuous variable and the other excluding Day 8 endpoint from the Westfall-Young analysis. Time-to-event endpoints will be excluded from both models.

A third analysis will provide adjusted P-values using Hochberg method. This analysis will include p-values from endpoints and will use p-value from multiple imputation where applicable. Results will be reported in [Table 45](#).

An additional global analysis will calculate Z-scores for all primary and secondary efficacy endpoints applicable to all subjects in the analysis population [3] and a global p-value will be calculated from the permutation test using z-scores from the linear model for continuous endpoints, cox model for time-to-event data, logistic regression for binary, and ordinal logistic regression model for continuous. For the logistic and log-rank test, the z-score can be calculated as the square root of the chi-square statistic of the treatment group variable from the adjusted model. A global test statistic vector will be constructed where each element is a Z score calculated from an endpoint in [Table 9](#).

The mean of the z-scores for all the endpoints will be calculated. A global p-value can then be obtained through a permutation test. Results of this global test will be reported in [Table 45](#).

Table 9: Endpoints to be included in the global analysis

Endpoint type	Endpoint
Primary	Ordinal score at Study Day 8
Key Secondary	Time (days) to sustained recovery
Key Secondary	Sustained survival without respiratory failure (binary: 1=Yes or 0=No)
Secondary	Time (days) to at least 1 units improvement from baseline/Time (days) to at least 2 units improvement from baseline
Secondary	Difference from baseline ordinal score at Days 3, 5, 8, 11, 15, 22, 29
Secondary	Number of days ordinal score > 4
Secondary	Number of days ordinal score > 5
Secondary	Number of days ordinal score > 6
Secondary	Number of days of hospitalization
Secondary	Value of CRP, ferritin, D-dimer, LDH, fibrinogen
Secondary (safety)	14-Day mortality, 28-Day mortality, 59-Day mortality (binary: 1=Yes or 0=No)
Secondary (safety)	Time (days) to death

Pseudocode:

Method 1: Obtain Adjusted P-values from Westfall-Young for Continuous and Binary Endpoints using observed data

```
proc multtest data=dataset perm stepboot n=100000 seed=1234;
  class trt;
  test mean (C1 C2 C3/uppertailed) ;
      test mean (C4 C5 ... Cx/lowertailed) ;
  test fisher(B1 B2 B3 B4/lowertailed);
  test fisher(B5 B6 ... Bx/uppertailed);
  contrast 'Trt vs Placebo' -1 1;
  ods output pValues=pvals;
run;
```

Where C1 C2 ... Cx is a list of all continuous covariates and C1 C2 ... Cx is the list of all binary covariates. The contrast should be updated as needed so that the placebo group is the reference. Note that the variables are grouped depending on the direction of the hypothesis test.

Method 2: Obtain Adjusted P-values using Hochberg method: Use raw p-values as input from the primary analysis for all the endpoints in [Table 9](#).

```
proc multtest data=rawpvalues hoc out=adj_pvals;
run;
```

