6. GENERAL STATISTICAL CONSIDERATIONS

6.1. General Principles

This is a proof of concept double-blind placebo controlled randomized trial testing a superiority hypothesis where interventions with a two-sided p-value $< .20$ will be declared promising and will be considered statistically significant if the final two-sided p-value is $< .05$. These data will be summarized by treatment (intervention name versus placebo) and when appropriate by baseline ordinal score. Additionally, data will be described according to the appropriate summary statistics, e.g.

- Percentages/proportions/odds ratios for categorical data. For tabular summaries of percentages/proportions, the denominator (e.g., number of subjects in the specified population) will be displayed.
- Means, standard deviation, median, and/or range for continuous data, median and confidence intervals for time-to-event data.

Confidence intervals will be generated; 95% and 80% confidence intervals will be generated for primary and key secondary outcomes. For hazard ratio and odds ratio estimates, Wald confidence intervals will be used. For confidence intervals of proportions for other efficacy and safety outcomes, Blaker confidence intervals will be used.

In general, all tables will have corresponding listings of data presented unless noted otherwise.

When calculating treatment effects (e.g., differences, hazard ratios, odds ratios) from regression modelling, placebo will be used as the reference group. Subjects on interventions will only be compared to control subjects who could potentially have been randomized to that intervention (i.e., they met eligibility criteria for the intervention and are at a site where the intervention was enrolling at the time of the subject's randomization). Analyses of newly added arm(s) will be performed comparing concurrently enrolled control subjects. For any modeling that uses covariates defined in Section 6.4, the category listed last for each variable in that section will be used as the control group for the interaction analysis and covariate-adjusted analyses.

For the time-to-event analyses, the following SAS pseudocode will be used to generate stratum-specific median time to event estimates and confidence intervals and stratum-specific Kaplan-Meier curves.

```
proc lifetest data=dataset plots=(s);
  time timevariable * censorvariable(1);
  test treatmentvariable;
run;
```

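### The code for the optional Table 44 runs one-tailed tests and names a bootstrap step-down, while the plan is otherwise two-sided and the text promises a permutation step-down

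*SAP*

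**What the plan says.** Section 6.8 states that the planned analyses are not adjusted for multiplicity. It then allows supplementary adjusted analyses if they look helpful for interpretation. For the first of these, adjusted p-values "will be computed using the Westfall-Young permutation approach", in its free step-down form, and go into Table 44. The table title also says permutation. The prose does not state sidedness.

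The Method 1 code opens with "proc multtest data=dataset perm stepboot n=100000 seed=1234". Each test statement that follows has a tail option. Continuous variables C1 to C3 are upper-tailed and the rest lower-tailed. Binary variables begin with "test fisher(B1 B2 B3 B4/lowertailed" and the rest are upper-tailed. A note below the code says: "Note that the variables are grouped depending on the direction of the hypothesis test".

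Elsewhere the plan is two-sided. Section 6.1 describes a superiority design "where interventions with a two-sided p-value $< .20$ will be declared promising", with two-sided 0.05 for statistical significance. Section 5 sizes the trial for a 2-tailed test. Section 8.1 sets OR = 1 against OR not equal to 1. For Table 45 (Hochberg), Section 6.8 says: "Use raw p-values as input from the primary analysis for all the endpoints" of Table 9.

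**The concern.** Tables 44 and 45 each print a raw p-value column for many of the same endpoints, including Day 8 status, survival without respiratory failure and 14-, 28- and 59-day mortality. The Table 45 values follow the plan's two-sided convention. The Table 44 values, if the code is followed, would be one-tailed, and the shell does not say so. A reader would naturally hold both columns against 0.05 or 0.20. On a one-tailed scale those levels correspond to two-sided 0.10 and 0.40. A favourable endpoint would look stronger in Table 44 than the plan's convention allows, and an unfavourable one would look unremarkable.

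The step-down keyword is a second, independent mismatch, since the code names a bootstrap and the text a permutation procedure.

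**Working it through.** **1. Which sidedness does the plan use?** Table 44 is a blank shell, so Table 5 is the nearest stated figure that can settle this. Inputs: the Table 4 distribution, 50 per arm at the interim (futile if OR < 1, efficacious if two-sided p < 0.001) and 100 per arm at the end. Method: a proportional-odds score test on 100,000 simulated trials per odds ratio.

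| True OR | Table 5 (.05 / .20) | Two-sided alpha | One-sided alpha |
|---|---|---|---|
| 1.00 | 0.026 / 0.096 | 0.025 / 0.096 | 0.049 / 0.181 |
| 2.00 | 0.765 / 0.913 | 0.762 / 0.909 | 0.844 / 0.950 |

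Table 5 is reproduced only with two-sided alpha.

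**2. Raw p-values.** For a t-test with the effect in the coded direction, one-tailed p = two-sided p / 2 exactly. Two Fisher examples with assumed counts, active versus placebo, lower-tailed:

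- 8/100 v 18/100: 0.0284 as coded, 0.0568 two-sided.
- 14/100 v 10/100: 0.862 as coded, 0.515 two-sided.

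**3. Smallest adjusted p-value.** Table 44 lists 20 endpoints: Day 8 status, survival without respiratory failure, 7 changes from baseline, 3 day counts, 5 markers and 3 mortality endpoints. The documents give no correlation, so take equicorrelated normal statistics over a range of rho. A raw two-sided p of 0.005 gives z = 2.807. With W standard normal, a = (z − √rho·W)/√(1 − rho) and b = (−z − √rho·W)/√(1 − rho):

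- as coded: 1 − E[Φ(a)^20]
- two-sided: 1 − E[(Φ(a) − Φ(b))^20]

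At rho = 0 these reduce to 1 − (1 − 0.0025)^20 = 0.0488 and 1 − (1 − 0.005)^20 = 0.0954. Numerical integration gives the other rows.

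| rho | Two-sided | As coded | Ratio |
|---|---|---|---|
| 0 | 0.0954 | 0.0488 | 0.51 |
| 0.3 | 0.0830 | 0.0415 | 0.50 |
| 0.5 | 0.0656 | 0.0328 | 0.50 |
| 0.7 | 0.0447 | 0.0223 | 0.50 |

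Up to rho = 0.5 the two versions fall on opposite sides of 0.05. At 0.7 both fall below it.

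**4. The whole step-down.** Simulation of 20 normal endpoints at 100 per arm, with 4,000 resamples and 150 data sets per scenario, independent or with correlations of 0.2 to 0.7. The effect sizes are assumptions.

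| Scenario | Share of endpoints with one/two-tailed ratio 0.45–0.60 | Share where one-tailed p is larger |
|---|---|---|
| +0.35 SD on all 20 | 82% | 0% |
| +0.35 SD on 12, −0.35 SD on 8 | 14–17% | 47–54% |
| No effect | 2–10% | 23–32% |

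For coded-direction effects with a two-sided adjusted p below 0.20, the median ratio was 0.50–0.52 when all endpoints benefit and 0.56–0.69 when effects are mixed. For effects against the coded direction in the same range of p, the one-tailed value was larger by a median factor of about 7 to 56.

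**5. Bootstrap versus permutation step-down.** In the same simulation the median ratio was 1.00, with a 5–95% range of at most about 0.80 to 1.22.

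**The case against.** Much of the case on the other side stands. The directional grouping is declared openly and the Section 6.8 prose never promises two-sided p-values for Table 44, so this is an unreconciled inconsistency and not a proven coding slip. The code is pseudocode with placeholder variables for an analysis that may never be run. Tables 44 and 45 would differ even with matching sidedness. Table 44 uses complete data, mean and Fisher tests without covariates, and Day 8 score as continuous. Table 45 takes the primary-analysis p-values, with multiple imputation for Day 8.

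A reader might also infer more than the documents support:

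- **That all Table 44 p-values are halved.** Steps 2 and 4 show otherwise. Halving needs an effect in the coded direction and, after adjustment, mainly a small p-value with endpoints leaning the same way.
- **That the bootstrap keyword contributes to the halving.** It does not (step 5). `perm` also stands in the same line, so permutation is not absent; only the step-down keyword disagrees. The documents do not say how the software treats the two together.
- **That harm on mortality would go undetected.** It is masked only in this table. Section 9.4 and Table 54 report mortality rates, differences and hazard ratios with 80% and 95% intervals and p-values through Days 15, 29 and 60.
- **That a trial conclusion could change at 0.05.** The SAP attaches no decision threshold to Table 44; its 0.20 and 0.05 limits classify the intervention on its final p-value.

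None of this removes the unlabelled difference in scale or the conflict between keyword and text.

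**Conclusion.** The point holds and is minor. As coded, Table 44 would report one-tailed raw and adjusted p-values in a plan whose hypotheses, sample size and thresholds are two-sided, without a label. The size is a factor of 2 on raw p-values in the coded direction and close to 2 on small adjusted p-values when effects agree in direction. Against the coded direction the p-values move the other way. The adjusted figures rest on 20 endpoints, normal test statistics and assumed correlations; at a raw p of 0.005 the ratio stays at 0.50 to 0.51 for rho from 0 to 0.7. The step-down keyword is a separate mismatch with little numerical effect, and it rests on reading `stepboot` as a bootstrap step-down. Table 44 is optional and does not determine whether the intervention is called promising or significant.

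**What to change.** Remove `uppertailed` and `lowertailed` from all Method 1 test statements, so that Table 44 is two-sided like the rest of the plan and the raw p-values in Table 45. Replace `stepboot` with the permutation step-down option, in line with the Section 6.8 text and the table title.

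If one-sided testing is intended, say so in Section 6.8 and in the Table 44 title, list the tail for each endpoint, and halve the reference levels (0.20/2 = 0.10 and 0.05/2 = 0.025). The list is needed because the code does not map endpoints to tails, and the sentence below it gives the same variable names to the continuous and the binary lists.

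The cost is a few words of code or a footnote. P-values for favourable effects become larger. Settle the choice before results are seen, since the analysis is run only if judged helpful.

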7. STUDY SUBJECTS

7.1. Disposition of Subjects

A summary of subject disposition and study milestones will be provided by treatment and actual baseline ordinal score in [Table 13](#). This summary will present the number of subjects screened, enrolled, randomized, completed all infusions of investigational agents, had any investigational infusions slowed or stopped, completed all expected blood draws, completed all expected NP swabs, completed Study Day 8, completed Study Day 15 visit, completed Study Day 22 visit, completed Study Day 29 visit, completed Study Day 60, and the number of subjects in each of the categories listed below.

- Safety Population
- ITT Population
- mITT Population
- Discontinuation of Treatment with reasons for discontinuation
- Completed the Study
- Did not complete the study with reasons for discontinuation of study

The denominator for the percentage calculation will be the total number of subjects who were in the analysis population corresponding to that treatment and ordinal score category.

A flowchart showing the disposition of study subjects, adapted from the Consort Statement [4] will be generated ([Figure 1](#)). This figure will present the number of subjects screened, randomized, lost to follow-up, and analyzed, by treatment group and actual baseline ordinal score (ordinal scale 5, 6, 7).

A listing will be provided by subject number, treatment assignment, actual baseline ordinal score, completion status and reasons for discontinuation of study product or study ([Listing 1](#)).

A listing of subjects who failed screening and reasons that subjects were screened but not randomized is provided in [Listing 2](#).

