The study will include one Master Protocol (DMID Protocol 20-0013: ACTIV-5/Big Effect Trial) and an additional “stage” for each investigational intervention included in the study. Stage-Specific Appendices will be provided, detailing the protocol interventions and any specific exceptions to the Master Protocol. One or more interventions/stages may be started at any time. The number of interventions/stages enrolling concurrently are programmatic decisions and will be based on the number of sites and the pace of enrollment. At the time of enrollment, subjects will be randomized to a stage, and then to either the active arm of that stage or the matching placebo. There will be approximately 100 subjects in each active arm of the platform trial (though this may be modified as specified in each stage-specific appendix to accommodate special circumstances). A given site will generally have no more than 3 interventions/stages at once.

See the schedule of assessments in each stage-specific appendix for assessment details. The schedule is similar to Adaptive COVID-19 Treatment Trial (ACTT) to allow evaluation of endpoints used in the larger study. Subjects will be assessed daily while hospitalized. Once subjects are discharged from the hospital, they will have a study visit on Study Days 8, 15, 22, 29 and 60 as an outpatient. The outpatient Study Days 8, 22 and 60 visits do not have laboratory tests or collection of samples and may be conducted by phone. Days 15 and 29 visits are preferred to be in person in order to collect safety laboratory testing, stored samples, and virologic assessments. However, if infection control considerations and other restrictions limit the ability to have visits at Study Days 15 and 29 in person, they may also be conducted by phone and only clinical data will be obtained.

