  ods output oddsratioswald = orest parameterestimates=pars;
run;
```

```
*Keep only estimates for the treatment variable;
```

```
data pars1;set pars;where Variable='Treatment variable';run;
```

```
*Combine estimates;
```

```
PROC MIANALYZE DATA=pars1;
  ODS OUTPUT PARAMETERESTIMATES= logor;
  MODELEFFECTS estimate ;
  STDERR stderr ;
```

```
RUN;
```

```
*Transform estimates from the log(OR) scale to the OR scale;
```

```
data OR;
  SET logor;
  OR_estimate = EXP(ESTIMATE);
  OR_LCL_95 =OR_estimate*EXP(-1.96*STDERR);
  OR_UCL_95 =OR_estimate*EXP(+1.96*STDERR);
  OR_LCL_80 =OR_estimate*EXP(-1.28*STDERR);
  OR_UCL_80 =OR_estimate*EXP(+1.28*STDERR);
```

```
RUN;
```

Similar pseudocode for odds ratio between the binary progression strata will use used for the Day 8 ordinal score endpoint analyzed by proportional odds using multiple imputation.

If the primary analysis results are at least borderline significant with a p-value < 0.10 and more than 5% of subjects have missing primary endpoint data, additional analyses will be performed to evaluate the effect of the missing data assumptions on the results. Using a tipping point strategy, these analyses will vary the Day 8 ordinal score independently across groups to determine if there is a distribution of missing data that would result in a change of conclusion.

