14.1 Description of Study Subjects

14.1.1 Disposition of Subjects

Table 13: Subject Disposition by Baseline Ordinal Score – ITT Population

Subject Disposition	Treatment A (N=X)								Treatment B (N=X)								All Subjects (N=X)							
	5 (N=X)		6 (N=X)		7 (N=X)		Any BOS ^a (N=X)		5 (N=X)		6 (N=X)		7 (N=X)		Any BOS ^a (N=X)		5 (N=X)		6 (N=X)		7 (N=X)		Any BOS ^a (N=X)	
	n/N	%	n/N	%	n/N	%	n/N	%	n/N	%	n/N	%	n/N	%	n/N	%	n/N	%	n/N	%	n/N	%	n/N	%
Randomized/Enrolled ^b	x/x	100	x/x	100	x/x	100	x/x	100	x/x	100	x/x	100	x/x	100	x/x	100	x/x	100	x/x	100	x/x	100	x/x	100
Safety Population ^c	x/x	xx	x/x	xx	x/x	xx	x/x	xx	x/x	xx	x/x	xx	x/x	xx	x/x	xx	x/x	xx	x/x	xx	x/x	xx	x/x	x
Discharged from Hospital	x/x	xx	x/x	xx	x/x	xx	x/x	xx	x/x	xx	x/x	xx	x/x	xx	x/x	xx	x/x	xx	x/x	xx	x/x	xx	x/x	x
Died During Follow-up	x/x	xx	x/x	xx	x/x	xx	x/x	xx	x/x	xx	x/x	xx	x/x	xx	x/x	xx	x/x	xx	x/x	xx	x/x	xx	x/x	x
Completed Follow-up (Study Day 1) – Hospitalized Subjects in Study ^f	x/x	xx	x/x	xx	x/x	xx	x/x	xx	x/x	xx	x/x	xx	x/x	xx	x/x	xx	x/x	xx	x/x	xx	x/x	xx	x/x	x
Ordinal Scale Data Available	x/x	xx	x/x	xx	x/x	xx	x/x	xx	x/x	xx	x/x	xx	x/x	xx	x/x	xx	x/x	xx	x/x	xx	x/x	xx	x/x	x
Safety Laboratory Blood Draw	x/x	xx	x/x	xx	x/x	xx	x/x	xx	x/x	xx	x/x	xx	x/x	xx	x/x	xx	x/x	xx	x/x	xx	x/x	xx	x/x	x
Secondary Research Blood Draw	x/x	xx	x/x	xx	x/x	xx	x/x	xx	x/x	xx	x/x	xx	x/x	xx	x/x	xx	x/x	xx	x/x	xx	x/x	xx	x/x	
OP Swab Collection	x/x	xx	x/x	xx	x/x	xx	x/x	xx	x/x	xx	x/x	xx	x/x	xx	x/x	xx	x/x	xx	x/x	xx	x/x	xx	x/x	x
PCR or Proteomic Assays Blood Draw	x/x	xx	x/x	xx	x/x	xx	x/x	xx	x/x	xx	x/x	xx	x/x	xx	x/x	xx	x/x	xx	x/x	xx	x/x	xx	x/x	x
Serum Blood Draw	x/x	xx	x/x	xx	x/x	xx	x/x	xx	x/x	xx	x/x	xx	x/x	xx	x/x	xx	x/x	xx	x/x	xx	x/x	xx	x/x	x
Repeat for Days 3, 5, 8, 11																								
Completed Follow-up (Study Day 15) – All Subjects in Study ^f	x/x	xx	x/x	xx	x/x	xx	x/x	xx	x/x	xx	x/x	xx	x/x	xx	x/x	xx	x/x	xx	x/x	xx	x/x	xx	x/x	x
Ordinal Scale Data Available	x/x	xx	x/x	xx	x/x	xx	x/x	xx	x/x	xx	x/x	xx	x/x	xx	x/x	xx	x/x	xx	x/x	xx	x/x	xx	x/x	x

Subject Disposition	Treatment A (N=X)								Treatment B (N=X)								All Subjects (N=X)							
	5 (N=X)		6 (N=X)		7 (N=X)		Any BOS ^a (N=X)		5 (N=X)		6 (N=X)		7 (N=X)		Any BOS ^a (N=X)		5 (N=X)		6 (N=X)		7 (N=X)		Any BOS ^a (N=X)	
	n/N	%	n/N	%	n/N	%	n/N	%	n/N	%	n/N	%	n/N	%	n/N	%	n/N	%	n/N	%	n/N	%	n/N	%
Safety Laboratory Blood Draw	x/x	xx	x/x	xx	x/x	xx	x/x	xx	x/x	xx	x/x	xx	x/x	xx	x/x	xx	x/x	xx	x/x	xx	x/x	xx	x/x	x

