Discontinued Treatment ^d	x/x	xx	x/x	xx	x/x	xx	x/x	xx	x/x	xx	x/x	xx	x/x	xx	x/x	xx	x/x	xx	x/x	xx	x/x	xx	x/x	x
Reasons for Discontinuation of Treatment ^e																								
XXXX	x/x	xx	x/x	xx	x/x	xx	x/x	xx	x/x	xx	x/x	xx	x/x	xx	x/x	xx	x/x	xx	x/x	xx	x/x	xx	x/x	x
XXXX	x/x	xx	x/x	xx	x/x	xx	x/x	xx	x/x	xx	x/x	xx	x/x	xx	x/x	xx	x/x	xx	x/x	xx	x/x	xx	x/x	x
Study Completion																								
Completed Study	x/x	xx	x/x	xx	x/x	xx	x/x	xx	x/x	xx	x/x	xx	x/x	xx	x/x	xx	x/x	xx	x/x	xx	x/x	xx	x/x	x
Did not Complete Study	x/x	xx	x/x	xx	x/x	xx	x/x	xx	x/x	xx	x/x	xx	x/x	xx	x/x	xx	x/x	xx	x/x	xx	x/x	xx	x/x	x
Reasons for Discontinuation of Study																								
XXXX	x/x	xx	x/x	xx	x/x	xx	x/x	xx	x/x	xx	x/x	xx	x/x	xx	x/x	xx	x/x	xx	x/x	xx	x/x	xx	x/x	x
XXXX	x/x	xx	x/x	xx	x/x	xx	x/x	xx	x/x	xx	x/x	xx	x/x	xx	x/x	xx	x/x	xx	x/x	xx	x/x	xx	x/x	x

BOS= Baseline Ordinal Score.
N=Number of subjects randomized/enrolled and in study for visits 1, 15, 22, 29, 60 and the number of subjects hospitalized and in study for visits 3,5, 8, and 11. Subjects that died or terminated early from the study on or prior to the study visit are not included in the denominators. n= Number of unique subjects that satisfy the row criteria.
^aThere were X additional subjects with an Actual Baseline Ordinal Score of 4 that are included in the ‘Any BOS’ summaries.
^b Represents the number of subjects who were randomized to either treatment arm.
^c Represents the number of subjects who received any amount of investigational agent.
^d Refers to the discontinuation of the investigational agent or placebo.
^eRefer to [Listing 1](#) for the individual reasons subjects discontinued or terminated early.
^f Visit completion is as completing a visit for that day or another day that is in window for the corresponding visit.

Programming

- Update milestones for each visit based on stage-specific schedule of events.
- Had any infusions stopped or slowed: if the question “Was full infusion administered successfully?” is marked “slowed or stopped” for either treatment, subject will be counted in this row.
- Completed all Required Investigational Infusions: if treatment was not discontinued, then subject will be counted in this row.
- Completed all Blood Draws: If there are not any blood draws that were “Not done”, then subject will be counted in this row.

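### SAP Section 7.1 and the Table 13 footnote give contradictory denominators, and at Day 8 the footnote's inpatient-only count keeps most missing primary-endpoint scores out of that table's rows

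*SAP*

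**What the plan says.** SAP Section 7.1 assigns a list of milestones to Table 13, among them "completed Study Day 8, completed Study Day 15 visit, completed Study Day 22 visit". It then gives a single rule for the percentages: "The denominator for the percentage calculation will be the total number of subjects who were in the analysis population". The rule is applied within each arm and baseline score group.

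The Table 13 shell (SAP Appendix 1, 14.1.1) does something else. Its first follow-up block is headed as covering hospitalised subjects in study and contains the row for availability of ordinal scale data. The shell instructs the programmer to "Repeat for Days 3, 5, 8, 11". A block covering all subjects in study starts only at Day 15. The footnote defines N for the inpatient days as "the number of subjects hospitalized and in study for visits 3,5, 8, and 11", and adds: "Subjects that died or terminated early from the study on or prior to the study visit are not included in the denominators".

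Day 8 is not an inpatient-only day. SAP Section 3.2 makes the Day 8 ordinal score the default primary endpoint. Section 4.1 says of discharged subjects that "they will have a study visit on Study Days 8, 15, 22, 29 and 60 as an outpatient". SAP Table 1 gives discharged subjects their own Day 8 window, Days 6 to 10.

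**The concern.** A programmer cannot satisfy both rules. If the shell is followed, as is likely, the row reporting how complete the Day 8 ordinal data are is calculated in a subset.

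The subset leaves out the groups in which a Day 8 score is most likely to be absent. Inpatients are scored daily, so gaps are likelier among discharged subjects who are not reached and subjects who have left the study. Under SAP Section 6.5, early terminators last known to be in hospital, or discharged to hospice, long-term acute care or another hospital, are multiply imputed. Subjects whose last known status is discharge elsewhere are assigned a score of 2. Neither group is in the Day 8 denominator.

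The denominator is also a post-randomisation outcome. A treatment that speeds discharge removes more of its own arm, so the completeness figures would not be comparable between arms.

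What is at stake is a reported completeness figure for the primary endpoint, by arm and baseline score. The primary estimate is not at stake.

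**Working it through.** **Inputs.** SAP Table 4, control arm at Day 8, categories 1 to 8: 0.0, 34.6, 1.2, 10.6, 17.1, 8.8, 24.2 and 3.5%, which sum to 100.0%. The sample size is 100 per arm (SAP Section 5).

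**Plan's own figure.** SAP Table 5 gives power at odds ratio 2 of 0.765 (alpha 0.05) and 0.913 (alpha 0.20). The Section 5 formula, solved for power, is Φ(λ√V − z), with V = 200(1 − Σp̄³)/12 and p̄ the average of the two arms' distributions.
- λ = ln 2 = 0.693 and Σp̄³ = 0.092, so V = 15.13 and λ√V = 2.696.
- Power is Φ(2.696 − 1.960) = 0.769 and Φ(2.696 − 1.282) = 0.921.
- A 10,000-replicate simulation of the two-look rule gives 0.756 and 0.906.

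Table 5 is reproduced within 2 points, so Table 4 and the shift are being read as intended.

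**Day 8 denominator, control.** Discharged: 0.0 + 34.6 = 34.6%. Dead: 3.5%. Outside the footnote's denominator: 38.1%. Inside: 61.9%.

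**Day 8 denominator, active arm at odds ratio 2.**
- Discharged: odds 0.346/0.654 = 0.529, doubled 1.058, probability 1.058/2.058 = 51.4%.
- Alive: odds 0.965/0.035 = 27.57, doubled 55.14, probability 55.14/56.14 = 98.2%, so 1.8% dead.
- Outside: 51.4 + 1.8 = 53.2%. Inside: 46.8%.

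Early terminators come off both figures as well.

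**What the row would show.** The documents give no rate of missing Day 8 scores, so the counts here are assumptions. Take 100 controls, about 62 of them in the footnote's denominator, and 10 missing scores. With deaths counted as known, the whole-population figure is 90/100 = 90% throughout.

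| Where the 10 missing scores lie | Table 13 row |
|---|---|
| All discharged and not reached | 62/62 = 100% |
| All terminated early while in hospital | 52/52 = 100% |
| Five discharged, five in hospital and in study | 57/62 = 91.9% |
| All in hospital and in study | 52/62 = 83.9% |

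The row can therefore overstate or understate completeness. It overstates when the gaps lie mainly outside hospital or among terminations, which is the likelier pattern.

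**Between-arm artefact.** Assume five missing inpatient scores per 100 in each arm. On the whole population both arms show 95%. On the footnote's denominators they show 57/62 = 91.9% for control and 42/47 = 89.4% for active at odds ratio 2.

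**The 5% condition.** Section 6.5.2 adds tipping-point analyses if the primary p-value is below 0.10 and "more than 5% of subjects have missing primary endpoint data", which for 200 subjects means more than 10. It does not say whether this is counted before or after the deterministic rules. Assume 9 missing per 100: five unreached subjects discharged to a location that qualifies for score 2, and four who withdrew in hospital. The proportion is 9% before the score-2 rule and 4% after it, on opposite sides of the threshold.

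**The case against.** The strongest reply is that missing Day 8 data can be found elsewhere. Tables 16 and 19 print n with a non-missing Day 8 score beside N for the mITT and ITT populations, with subgroup rows for baseline score 5 and for 6 or 7. Table 13 has study-completion rows with reasons. Figure 1 shows loss to follow-up. Table 11 counts missed visits by arm and baseline score. Listings 1, 3 and 13 hold subject-level detail. Table 13 also prints n/N, so its reduced N is visible.

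Most of that stands. A reader might infer that missing Day 8 scores cannot be seen at all; the documents do not support this. A gap in an inpatient still in study would show in Table 13, and the rest can be partly reconstructed. But no table gives observed against missing Day 8 scores by arm over all subjects. Table 16 does not say whether n precedes the score-2 and last-observation rules, and its subgroup rows use the filled-in complete data. The completion rows and Figure 1 are not specific to Day 8: a discharged subject who misses Day 8 and answers later still completes the study. Table 11 does not name the visit.

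A reader might also infer that Table 13 feeds the imputation or the 5% trigger. It does not. Imputation follows subject-level rules, and Section 6.5.2 does not cite the table.

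Finally, Table 13 is a master template whose milestones are to be updated by stage, and stage-specific elements supersede it. That is a route for the correction. It does not settle which denominator applies here.

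**Conclusion.** The contradiction is in the text, and for the Day 8 ordinal score the footnote's denominator is unsuitable. It leaves out about 38.1% of controls and, at odds ratio 2, about 53.2% of the active arm, plus early terminators in both. Most missing Day 8 scores would therefore be absent from Table 13's Day 8 rows. The word most rests on gaps arising chiefly after discharge or through termination, because inpatients are scored daily. The percentages rest on Table 4 holding and on proportional odds for the shift. They size the denominator, not the amount of missing data, which the documents do not give; Section 6.5.1 expects it to be small and plans chart review.

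The rows for Days 15, 22, 29 and 60 also depart from Section 7.1, since the footnote drops deaths and terminations there too, but they include discharged subjects.

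This is a reporting defect that should be corrected. Nothing in power, sample size or the primary model changes.

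**What to change.** 1. **Table 13, Day 8 rows for completed follow-up and ordinal data available.** Use all subjects in the analysis population by arm and baseline ordinal score: ITT, as the table is titled, with the mITT count also shown because mITT is the default primary population. Count deaths as known (score 8), keep early terminations in the denominator as missing, and show in hospital, discharged and terminated separately.
2. **Other Table 13 rows.** Keep the inpatient denominator for laboratory, swab and blood-draw rows on Days 3 to 11, and for the ordinal rows on Days 3, 5 and 11, when no outpatient visit is scheduled.
3. **Section 7.1.** Amend the denominator sentence to state these exceptions and to cover the rows for Days 15 to 60.
4. **Table 16.** Label n as the number with an observed Day 8 score before any imputation.
5. **Section 6.5.2.** State that the 5% trigger uses the overall mITT proportion with no observed Day 8 score, before the score-2, last-observation and multiple-imputation rules.

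The cost is a footnote, a few table rows and short edits to two sections and one label. No new data are needed. The reported completeness is likely to look less favourable.
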